Official Title: Safety and feasibility of Early Oral Nutrition after Endoscopic Treatment for Patients with Liver Cirrhosis: A Historical-prospective, Comparative Effectiveness study

NCT number: NCT04823780

Document date: September 1, 2020

Study protocol

The purpose of the study was to compare safety and effectiveness of different feeding time in the real-world clinical practice. Detailed history-taking and physical examination were carried out on all recruited patients and basic information were recorded including liver function by Child-Pugh's scores and MELD scores, endoscopic features. EVL was performed after confirmation of esophageal varices and cyanoacrylate was injected if gastric varices were diagnosed. Further, the octreotide was given for 24 hours postop routinely. All the therapeutic endoscopies were performed by a technically proficient gastrointestinal endoscopist. The endoscopist, data collectors and statisticians were blinded to the follow-up dietary intervention tasks.

Eligible patients in the EN group were required to fast for 4 hours following endoscopic treatment and peptisorb produced by Milupa Nutricia GmbH was used for enteral nutrition at the beginning. The initial recommended dose of peptisorb is 60 g dissolved in 250ml water, which can provide 250 kcal energy (protein 9.8 g, fat 2.45 g, carbohydrate 46.5 g). Transition to soft diet such as chicken custard could be carried out after 2 to 3 times of giving peptisorb emulsion if there were no adverse reactions. Further, it is recommended that the diet of patients should obey the principle of multiple-meal-with-small-amount-for-each and the daily meals could up to between 4 and 5 times. The time and amount of diet was recorded specifically and the total energy intake through enteral nutrition were calculated. Extra energies were supplemented by parenteral nutrition. All patients required fasting for at least 48 hours in the control group and parenteral nutrition was provided through intravenous infusion, then transit gradually from liquid diet to soft diet. All nutritional supports were provided based on the standard recommended by ESPEN guideline on clinical nutrition in liver disease that calorie requirement for $30 \sim 35 \text{ kcal} \cdot \text{kg}^{-1} \cdot \text{d}^{-1}$.

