In addition, the prospectively enrolled patients in interventional group were divided into three subgroups according to dietary time. The early enteral nutrition (EEN) in the current study was defined as starting enteral nutrition between 4 and 12 hours after endoscopic therapy and delayed enteral nutrition (DEN) was defined as between 12 and 48 hours. The dietary time after 48 hours was defined as parenteral nutrition (PN).

Outcomes and definitions

The primary endpoint of this study was variceal re-bleeding following endoscopic treatment. The secondary endpoints were mortality whereas the adverse events during the 42-day follow-up. The days and expenses of hospitalization were also compared between the two groups in this study. Besides, inflammatory factor, serum albumin level, defecation time and the satisfaction with nutritional support of patients were also evaluated in the three subgroups.

Variceal Re-bleeding includes very early rebleeding and early rebleeding. In this study, very early rebleeding was defined as rebleeding within 5 days after endoscopic treatment whereas early rebleeding was defined as within 5 and 42 days after endoscopic treatment. Rebleeding within 48 hours was considered as failure treatment. Whatever anytime, once the rebleeding occurred, the patients would receive pharmacotherapy or endoscopic treatment again.

Satisfaction of the patients with nutritional support was assessed based on 5 - point Likert scale of very satisfied (5 points), satisfied (4 points), neither satisfied nor dissatisfied (3 points), dissatisfied (2 points) and very dissatisfied (1 point). The satisfaction rate was regarded as the proportion of very satisfied and satisfied.

Statistical analysis

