Statistical analyses were performed using statistical software IBM SPSS Statistical 26.0 (SPSS, Chicago, IL). The baseline data of control group and intervention group were matched using propensity score analysis (PSM) in a ratio fashion of 1:1 using the nearest neighbor technique. Quantitative variables conforming to normal distribution were expressed as mean \pm standard deviation ($M \pm SD$) whereas the variables not conforming to normal distribution were presented as median (interquartile range (IQR), (P25, P75)). Qualitative variables were expressed as percentages. Quantitative variables were compared using Student's *t*-test, Mann-Whitney nonparametric test or variance analysis, and χ^2 test. On the other hand the Fisher's exact tests were used to compare qualitative variables in this study. Linear regression analysis was performed to find the significant factors influencing diet time after endoscopic treatment. The analysis of outcomes between the two groups was conducted based on intention-to-treat

(ITT) and per-protocol (PP) analysis. $P < 0.05$ was considered statistically significant.

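### Hospital expenses are compared between cohorts that appear to come from different calendar periods, with no price year stated, so any price change would count as an effect of feeding time

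*Combined protocol and SAP*

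**What the plan says.** All references are to the Combined protocol and SAP.

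- **Design.** The official title calls the trial "A Historical-prospective, Comparative Effectiveness study".
- **Which group is prospective.** The Study protocol section says that "the prospectively enrolled patients in interventional group were divided into three subgroups according to dietary time". It describes the comparator only by its feeding rule: "All patients required fasting for at least 48 hours in the control group".
- **Outcome.** Under Outcomes and definitions, after the primary endpoint (variceal re-bleeding) and the secondary endpoints, the plan adds: "The days and expenses of hospitalization were also compared between the two groups in this study".
- **Adjustment between groups.** Under Statistical analysis: "The baseline data of control group and intervention group were matched using propensity score analysis (PSM) in a ratio fashion of 1:1". The matching covariates are not listed.
- **Tests.** Quantitative variables are compared by t-test, "Mann-Whitney nonparametric test or variance analysis". The one regression model has a different outcome: "Linear regression analysis was performed to find the significant factors influencing diet time after endoscopic treatment".

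The document gives no accrual dates, currency, price year, deflator, fixed unit costs or calendar-period term.

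**The concern.** A hospital bill is resource use multiplied by price. Feeding time can change the first factor. The second depends on when the patient was admitted. If all controls were admitted in an earlier period and all intervention patients in a later one, group and period are the same variable, and the expense difference mixes any effect of feeding time with any change in prices.

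Matching does not help. In every matched pair one bill would come from each period, so a price change shifts every pair in the same direction. A larger sample does not help either: the shift stays the same while the standard error falls, so a purely price-driven difference becomes more likely to reach P < 0.05. The intention-to-treat and per-protocol analyses would share the problem.

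At stake is the economic message. Rising prices would make the later intervention group look dearer and could hide a real saving. Falling prices could create an apparent saving where there is none.

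**Working it through.** **There is no figure to reproduce.** The document gives no expense mean or SD, sample size, dates or price data. Every numerical input below is an assumption, shown as a range.

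**Step 1: do group and period coincide?** The title says part of the data are historical. The Study protocol section says the intervention group was enrolled prospectively. The historical part is then most naturally the control group. This is an inference, since no sentence says so outright. If only some controls were historical, the shifts below would shrink in proportion.

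**Step 2: spurious shift in mean expense.** With annual price change r and a gap of g years, identical resource use gives a later bill that differs from the earlier one by (1 + r)^g - 1.

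| r per year | g = 1 | g = 2 | g = 3 | g = 5 |
|---|---|---|---|---|
| +5% | +5.0% | +10.3% | +15.8% | +27.6% |
| +3% | +3.0% | +6.1% | +9.3% | +15.9% |
| +2% | +2.0% | +4.0% | +6.1% | +10.4% |
| 0% | 0% | 0% | 0% | 0% |
| -2% | -2.0% | -4.0% | -5.9% | -9.6% |
| -5% | -5.0% | -9.8% | -14.3% | -22.6% |

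Rises and cuts are not mirror images: 1.05^5 - 1 = +27.6%, but 0.95^5 - 1 = -22.6%.

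**Step 3: chance of a significant difference when feeding time has no effect.** Let d be the shift as a fraction of mean expense, and se = CV × sqrt(2/n) for n per group. With two-sided alpha 0.05 (the plan does not state sidedness), the probability is Phi(d/se - 1.96) + Phi(-d/se - 1.96). The CV is assumed to be 0.4 to 0.6.

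Example: n = 100, CV = 0.4, d = 0.10. Then se = 0.4 × sqrt(0.02) = 0.0566 and d/se = 1.768, so the probability is Phi(-0.192) + Phi(-3.728) = 0.424.

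| Shift | n = 50 per group | n = 100 | n = 200 |
|---|---|---|---|
| 0% | 5% | 5% | 5% |
| 5% | 7.0-9.6% | 9.1-14.3% | 13.3-24.0% |
| 10% | 13.3-24.0% | 21.8-42.4% | 38.5-70.5% |
| 15% | 24.0-46.6% | 42.4-75.5% | 70.5-96.3% |

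In each cell the lower figure is for CV 0.6 and the higher for CV 0.4.

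**Step 4: after conversion to one price year.** If the index follows the hospital's prices, the price component is zero and the false-positive rate from this source returns to 5%. If it does not, a residual remains. Suppose the index rises 3% a year over 3 years:

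- Tariffs rise 5% a year: 1.05^3 / 1.03^3 - 1 = 1.1576 / 1.0927 - 1 = +5.9%, against +15.8% unadjusted.
- Tariffs do not change: 1 / 1.0927 - 1 = -8.5%, against 0% unadjusted.

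A badly chosen index can therefore add error, which is why the unadjusted result should also be shown.

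**The case against.** The strongest reply is that this is a gap in the description and not a demonstrated bias. A reader might infer that the plan compares nominal bills at face value and that the result is therefore biased, with only the size unknown. The document does not support that. It does not say whether bills were nominal, standardised or repriced; it is silent. It gives no dates, so the gap may be short, and if prices did not move the bias is zero. The historical status of the controls is itself inferred. All of this stands, and the point has to be put conditionally.

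The size is also open to challenge. The +28% end needs 5% growth and a 5-year gap together, and nothing in the document anchors either. Much of the assumed grid lies at 2-6%, and a 5% shift with 50 per group raises the false-positive rate only to 7.0-9.6%. That stands too: the range shows what could happen and is not an estimate for this trial.

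Nor does the concern reach the main result. Expenses are an additional comparison, neither the primary endpoint nor a named secondary one. Days in hospital, compared in the same sentence, are not subject to price change, though changes in practice could affect them.

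The reply does not show that the plan guards against the problem. Baseline matching and unadjusted tests cannot separate price from feeding time, and without dates or a price year a reader cannot tell whether the comparison is sound. The concurrent prospective subgroups do not fill the gap: expenses are not among the outcomes listed for them, and feeding time is not described as randomised.

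**Conclusion.** The point holds in conditional form and at low severity. The control group appears to be historical and the intervention group prospective. The plan compares their hospital expenses with no stated price year or price adjustment, so any price change between the periods would be counted as an effect of feeding time.

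On assumed inputs (2-5% a year over 1-5 years) the spurious difference is +2% to +28% for rising prices and -2% to -23% for falling ones. With stable prices it is zero. Neither direction nor size can be settled from the document. The conclusion rests on the inference that the controls are historical, and on the plan's silence about price adjustment being a real absence. It concerns the expenses comparison only and leaves the re-bleeding conclusion untouched.

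**What to change.** Under Statistical analysis:

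1. State the accrual period of each cohort, and say explicitly whether the controls are historical.
2. Before comparing expenses, convert every bill to one stated price year with a named health-price index applied by admission year.
3. Report the unadjusted expenses as a sensitivity analysis.
4. Reprice resource use at one fixed tariff list only if itemised bills exist; the document does not mention them.

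**Cost.** The index route takes a sentence or two in the SAP and a deflator by admission year. It uses existing bills and admission dates and needs no new patient data. Repricing would take more work.

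**Downsides.** The choice of index must be justified and may not follow this hospital's tariffs. Deflation removes price change only. Changes in practice between the periods, which alter resource use itself, would remain and should be acknowledged when the expenses result is interpreted.

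### Satisfaction is scored 1 to 5 across three ordered feeding-time subgroups, but the only summary defined is the proportion scoring 4 or 5, which gives up power that a trend or ordinal test on the full score would keep

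*Combined protocol and SAP*

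**What the plan says.** The Study protocol section forms the groups: "the prospectively enrolled patients in interventional group were divided into three subgroups according to dietary time". EEN and DEN are defined by "starting enteral nutrition between 4 and 12 hours after endoscopic therapy and delayed enteral nutrition (DEN) was defined as between 12 and 48 hours", and PN covers feeding after 48 hours. The three subgroups are therefore ordered by time to first feeding.

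Under Outcomes and definitions, four measures are assigned to this three-way comparison: "inflammatory factor, serum albumin level, defecation time and the satisfaction with nutritional support of patients were also evaluated in the three subgroups". For satisfaction, "Satisfaction of the patients with nutritional support was assessed based on 5 - point Likert scale", with 5 the best score and 1 the worst. The one summary then defined is a two-level rate: "The satisfaction rate was regarded as the proportion of very satisfied and satisfied".

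The Statistical analysis section is a general list for the whole study. For quantitative variables it gives Student's t-test, then "Mann-Whitney nonparametric test or variance analysis". Chi-square and Fisher's exact tests are also named. The threshold is P < 0.05. The section does not say which test applies to satisfaction. It names no three-group rank test, trend test or ordinal model, and gives no rule for pairwise follow-up.

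**The concern.** A five-level ordered score cut to yes or no loses the distinction between 5 and 4 and all distinctions among 3, 2 and 1. If most patients are content, nearly all of them fall on one side of the cut and the rate has little left to show. A 3x2 chi-square or Fisher test on that rate also treats EEN, DEN and PN as unordered labels, although the question is whether satisfaction changes as feeding is delayed. Both losses make a real gradient harder to detect, and both can be avoided with data the plan already records.

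A smaller gap lies beside this. The plan foresees variables that are not normally distributed and assigns outcomes such as defecation time to three subgroups, but the only rank test it names, Mann-Whitney, compares two samples.

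**Working it through.** The plan states no power, sample size or expected satisfaction figure, so there is nothing of its own to reproduce. From the documents come three ordered subgroups, a 1-5 score, a cut at 4, and a threshold of 0.05 (taken as two-sided, which is not stated). Everything else below is assumed: equal subgroups, proportional odds, the PN distribution and the effect size.

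**1. Information kept by the cut.** Under proportional odds and small effects, the efficiency of the 4-5 versus 1-3 cut relative to the full score is p(1-p) / [(1 - Σp_k³)/3], where p is the satisfied proportion and p_k are the five category proportions. Take PN scores 1 to 5 as 5/10/30/35/20%:
- p = 0.35 + 0.20 = 0.55, so p(1-p) = 0.2475.
- Σp_k³ = 0.000125 + 0.001 + 0.027 + 0.042875 + 0.008 = 0.079, so (1 - 0.079)/3 = 0.307.
- Ratio = 0.2475 / 0.307 = 0.81.

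For other assumed distributions the ratio is 0.77 with 40% satisfied, 0.80 with 55%, 0.64 with 75% and 0.33 with 90%.

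**2. Power with that PN distribution.** Assume steps of 0.4 log-odds from PN to DEN and from DEN to EEN, so the EEN-versus-PN odds ratio is exp(0.8) = 2.23. The satisfied proportions are then 55% in PN, 65% in DEN and 73% in EEN. With 50 per subgroup, simulated power is:
- 3x2 chi-square on the rate: about 0.39.
- Kruskal-Wallis on the 5-point score: about 0.47 (0.47 to 0.49 across simulation runs).
- Rank trend test on the 5-point score: about 0.59.

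Kruskal-Wallis against chi-square is about 0.30 against 0.23 with 30 per subgroup, and about 0.69 against 0.56 with 80.

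**3. Power across other satisfaction levels.** Here there are 50 per subgroup, the EEN-versus-PN odds ratio is 2, and DEN is midway on the log-odds scale. Trend tests here are linear tests over the ordered subgroups.

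| Satisfied in PN | Chi-square 3x2, rate | Trend, rate | Kruskal-Wallis, 5-point | Trend, 5-point |
|---|---|---|---|---|
| 40% | 0.306 | 0.426 | 0.378 | 0.475 |
| 55% | 0.30 | not tabulated | 0.38 | not tabulated |
| 75% | 0.207 | 0.271 | 0.360 | 0.419 |
| 90% | 0.113 | 0.147 | 0.331 | 0.385 |

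At 40% satisfied, using the order of the subgroups helps more than using the full score. At 75% and 90% the full score helps more. The trend test on the full score does best in every tabulated row. With an odds ratio of 3, chi-square, Kruskal-Wallis and 5-point trend give 66, 77 and 84% at 40% satisfied; 41, 74 and 78% at 75%; and 18, 68 and 72% at 90%.

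**4. False positives.** With no true difference, each single overall test holds its level: 3x2 chi-square 4.2-5.3%, Kruskal-Wallis 4.7-5.2%, 5-point trend 4.6-5.3%. Three unadjusted pairwise tests would give 1 - 0.95³ = 14.3% if independent. Allowing for the correlation between comparisons of equal groups, the figure is 12.2%. Simulated pairwise Mann-Whitney tests on the score give 11.5-12.7%.

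**The case against.** The strongest reply is that the plan does less wrong than it may seem. A reader might infer that, because Mann-Whitney is the only rank test listed, the plan commits to three unadjusted pairwise tests and so to a false-positive rate of about 12%. The documents do not support that. Pairwise testing is stated nowhere. The list serves the whole study, including two-group comparisons for which Mann-Whitney is suitable. For the satisfaction rate, chi-square or Fisher's exact test on a 3x2 table is available and is a single overall test at about 5%; variance analysis is likewise a three-group test. What remains is silence about skewed outcomes in three subgroups, which a competent analyst would probably fill sensibly.

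A reader might also infer that the raw score will go unanalysed. The plan does not say so; it defines the rate and specifies no analysis of the score. The proportion in the top two categories is a common and readable summary, and nothing is wrong with reporting it.

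Three further points stand. The power figures rest wholly on assumed sizes, distributions and effects, so no fixed loss can be attributed to this trial. The trend-test gain assumes that satisfaction moves in one direction from EEN to PN; a non-monotone pattern would reduce or remove it. Finally, no randomisation to the subgroups is described, and the Statistical analysis section itself models factors influencing diet time. A more powerful test would not make a gradient across them causal evidence of benefit.

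None of this gives a reason to prefer the two-level rate as the tested outcome once the five-level score has been recorded.

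**Conclusion.** The point holds as a cost-free improvement to an additional outcome. Defining only the rate gives up ordinal information, and none of the listed tests uses the order of the subgroups when applied to it. At 50 per subgroup, with an odds ratio of 2 to about 2.2 and 40-90% satisfied in PN, power is about 11-39% on the rate against 33-47% for Kruskal-Wallis on the score. The rank trend test reaches about 59% in the 55% scenario with odds ratio 2.23. The loss is modest when about half of patients are satisfied and large when most are. These figures assume equal subgroups and proportional odds, neither of which comes from the documents.

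The false-positive figure of about 12% describes what unadjusted pairwise tests would do if run alone. It is not a property of the plan as written, and supports only a clarification of wording.

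Re-bleeding is the primary endpoint, and mortality and adverse events are the secondary ones. Their conclusions are not touched.

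**What to change.** In the Statistical analysis section, name one test on the full 5-point score as the satisfaction analysis: either a Jonckheere-Terpstra trend test or a proportional-odds model across EEN, DEN and PN, chosen before the data are examined. Keep the satisfaction rate, by subgroup, as a descriptive summary.

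As a clarification, name Kruskal-Wallis as the overall test for other skewed three-subgroup outcomes, with pairwise Mann-Whitney tests only if it is significant. With three groups, that gate is enough to hold the family-wise error near 5%. If all three subgroups are alike, the overall test guards the level; if only two are alike, just one pairwise test can be falsely positive.

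The cost is a few sentences in the analysis plan. No extra patients, measurements or changes in conduct are needed.

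### The 1:1 matching has no stated caliper, replacement rule or balance check, and the named outcome tests ignore pairs and covariates, so P values may be too large or too small

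*Combined protocol and SAP*

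**What the plan says.** The matching is described in one sentence of the Statistical analysis section: baseline data of the two groups were "matched using propensity score analysis (PSM) in a ratio fashion of 1:1 using the nearest neighbor technique". No caliper, replacement rule, covariate list or balance check follows.

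For quantitative variables the section names Student's t-test, without saying whether it is paired, and then "Mann-Whitney nonparametric test or variance analysis". For qualitative variables it names chi-square and Fisher tests: "exact tests were used to compare qualitative variables in this study". The threshold is P below 0.05, with sidedness not given. The only regression is not an outcome model: "Linear regression analysis was performed to find the significant factors influencing diet time after endoscopic treatment".

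Under Outcomes and definitions, rebleeding is the primary endpoint. Of the resource outcomes the text says: "The days and expenses of hospitalization were also compared between the two groups in this study". Outcomes are to be analysed by intention to treat and per protocol, but the section does not say whether either set is the matched set.

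**The concern.** Matching has two consequences that the outcome analysis should respect.

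- **Similar pairs.** If the matching covariates predict the outcome, partners are positively correlated. An independent-samples test then overstates the standard error of the difference.
- **Matching options.** Without a caliper, the last patients to be matched may get poor partners, or the pool may be too small to offer any choice. If controls are reused, the same person is counted several times as if independent.

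The first consequence costs power, mainly for hospital days and expenses. The second can produce false positive findings, including on the primary endpoint, and poor matches also distort the means, medians and percentages that the plan reports. The plan does not let a reader tell which case applies.

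**Working it through.** **Inputs.** From the document: 1:1 nearest-neighbour matching, the tests listed above, and a 5% level (taken as two-sided). Everything else is assumed. The plan has no figure of its own to reproduce.

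**1. Controls used once, good balance.** With within-pair outcome correlation ρ, the true variance of the difference is (1 − ρ) times what the unpaired test assumes. Its actual size is 2 × [1 − Φ(1.96/√(1 − ρ))].

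| ρ | 1.96/√(1 − ρ) | actual size |
|---|---|---|
| 0.05 | 2.01 | 4.4% |
| 0.1 | 2.07 | 3.9% |
| 0.2 | 2.19 | 2.8% |
| 0.3 | 2.34 | 1.9% |

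Simulations used a logistic propensity score on three covariates, greedy matching, 100 intervention patients, pools of 100 to 400 controls and a 0.2 SD caliper.

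- At 10–30% of outcome variance explained, t-test size was mostly 2–4%, with values up to 5.0% at 10%.
- Chi-square for rebleeding (8–15% risk) had size 2.8–5.1%.
- Power for a 0.35 SD difference with about 86 pairs was 62% (unpaired t) against 64% (covariate-adjusted regression) at 10% explained. At 30% it was 63–67% against 74%.
- If the covariates explain nothing, nothing is lost.

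**2. Controls used once, no caliper.** The limiting case is a pool no larger than the intervention group: 100 and 100. Every control is then used, and the matched comparison is the crude one. Assume a 0.5 SD baseline shift and covariates explaining 5% or 20% of variance. The expected bias is 0.5 × √0.05 = 0.112 SD or 0.5 × √0.20 = 0.224 SD; simulation gave 0.112 and 0.229. The standard error is √(2/100) = 0.141 SD, so the simulated biases are 0.79 and 1.62 standard errors. Size is Φ(δ − 1.96) + Φ(−δ − 1.96), where δ is that ratio:

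- δ = 0.79: 12.4% (simulated t-test 12.8%, chi-square 8.1%, Fisher 5.5%)
- δ = 1.62: 36.7% (simulated t-test 37.3%, chi-square 18.3%, Fisher 14.1%)

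Other no-caliper results:

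- Pools of 120 or 200, 0.6 SD shift: bias 0.03–0.20 SD, t-test 3.8–31%, chi-square 6–21%.
- Pool of 120 with residual imbalance of 0.54 SD: t-test 55%.
- Pool of 300, 0.5 SD shift: t-test 3.2–4.5%, so no inflation.

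A 0.2 SD caliper brought the 100-and-100 t-test back to 4.5% and 3.7%. A paired t-test did not cure the bias (13.2% and 39.8%).

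**3. Controls reused.** Let w be the number of times a control is used and D = Σw²/n for n pairs. With ρ ignored, size is 2 × [1 − Φ(1.96 × √(2/(1 + D)))].

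| D | critical value | actual size |
|---|---|---|
| 1.25 | 1.85 | 6.5% |
| 1.5 | 1.75 | 8.0% |
| 2 | 1.60 | 11.0% |
| 3 | 1.39 | 16.6% |

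Simulated without a caliper at 5–20% explained variance:

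- 100 controls: t-test 11.9–15.1%, chi-square 12.4–18.3%
- 300 controls: t-test about 6–8%, chi-square 8.5–8.9%

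Inflation is not certain. With 300 controls, no shift and 40% explained, the t-test was at 3.1–3.8% and chi-square at 5.4–6.0%. A standard error using the control weights gave 3.5–4.9% at 5–20% explained variance.

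**The case against.** Four objections carry weight.

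- **Natural reading.** The text says that baseline data were matched. It does not say outright that outcomes are tested in the matched set. If the intention-to-treat analysis used all patients, the pairing issue would fall away, though the matching would then serve no purpose for outcomes. The form of the t-test is also open.
- **Reuse is hypothetical.** A reader might infer from the silence that controls were reused. Nothing in the section suggests it, and single use is the ordinary reading of 1:1.
- **Small effect under good matching.** With single use and a caliper, ignoring the pairs alone costs 0–3 points of power at 10% explained variance and 0–8 at 30%, on outcomes listed after the primary and secondary endpoints.
- **Overreach in the remedy.** Under those same conditions the rebleeding tests are near nominal, so they need not be replaced. Pair-clustered standard errors added nothing visible: the adjusted model had size 4.5–5.0% without them (pool of 200) and 4.7–6.6% with them.

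These limit the point without removing it. A reader might also infer the comforting version: that unpaired tests after matching are merely conservative, that only P values are touched, and that the rebleeding conclusion is safe. The plan does not support that either, because each part requires good balance, and the plan commits to neither a caliper nor a balance check.

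**Conclusion.** The gap is real and minor. On the natural reading, no two-group outcome analysis uses the pairs or the matching covariates, and the options that decide the direction of error are unstated.

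- **Single use, good balance:** t-test size about 2–4% at 10–30% explained variance for days and expenses; rebleeding near nominal or slightly conservative.
- **Single use, no caliper, small pool:** biased group differences. Size is about 13–37% for the t-test in the smaller-pool scenarios, higher under larger assumed shifts, and about 8–21% for chi-square. This error comes from poor matches, not from ignoring pairs.
- **Reuse:** tests can be too liberal, but not in every scenario.

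These are illustrations, not estimates for this trial: group sizes, baseline shift, event risk and covariate strength are all assumed. The plan cannot be said to have produced a false result.

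The feeding-time subgroups are outside the point. The text says that "the prospectively enrolled patients in interventional group were divided into three subgroups according to dietary time"; they are not matched to one another, so independent-sample tests do not ignore any pairing there.

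**What to change.** 1. State that matching is without replacement and within a caliper, for example 0.2 SD of the logit propensity score. List the covariates and report standardised differences after matching.
2. State that the two-group outcomes are compared in the matched set.
3. Analyse matched hospital days and expenses by regression on group plus the matching covariates, using the baseline data already recorded (Child-Pugh, MELD, endoscopic features), on a log scale if skewed. Pair-clustered standard errors are optional. In one set of single-use runs, covariate adjustment gave size 3.0–6.0%.
4. For rebleeding, report the risk difference and keep the chi-square or Fisher test. Add a propensity-score-adjusted estimate if events allow.
5. If controls were in fact reused, weight each control by its number of uses and take a patient-level robust standard error. Covariate adjustment alone did not cure reuse. The weighted version was mostly near nominal, but one run with a pool of 120 still gave 7.1%.

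The cost is a few lines of text and slightly more analysis. With a caliper, roughly 3 to 28 of 100 intervention patients went unmatched under the assumed inputs, so the result describes matchable patients only. A log-linear model reports a ratio instead of a difference.

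### The only listed three-group test for quantitative outcomes is an unspecified analysis of variance, with no safeguard against unequal spread, although the feeding-time subgroups have uncontrolled sizes

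*Combined protocol and SAP*

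**What the plan says.** Under Study protocol, "the prospectively enrolled patients in interventional group were divided into three subgroups according to dietary time": EEN (feeding begun 4 to 12 hours after endoscopy), DEN (12 to 48 hours) and PN (after 48 hours). No size is planned for any of them.

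Under Outcomes and definitions, "inflammatory factor, serum albumin level, defecation time and the satisfaction with nutritional support of patients were also evaluated in the three subgroups". The first three are quantitative. Satisfaction is scored on a five-point scale and summarised as a proportion.

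Under Statistical analysis, the methods for quantitative variables form one list: Student's t-test, then "Mann-Whitney nonparametric test or variance analysis". The list does not say which test serves the three-subgroup comparison or which version of ANOVA is meant. Normality is the only distributional criterion, and it decides how data are summarised: "Quantitative variables conforming to normal distribution were expressed as mean" with SD, otherwise median and IQR. Nothing is said about equality of variances, about a rank test for more than two groups, or about pairwise follow-up. A P value below 0.05 "was considered statistically significant".

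**The concern.** Student's t-test and the classical ANOVA F test pool one variance across groups. With equal group sizes this does little harm. With unequal sizes the result depends on which group is the more variable. If a small group has the largest spread, the pooled variance understates the noise in that group's mean and the test rejects too often. If the largest group has the largest spread, the test rejects too rarely and loses power.

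The design leaves the subgroup sizes to chance, because membership follows from when feeding started. Patients in the EN group were to fast for 4 hours and then be fed, so feeding after 48 hours departs from that schedule and the PN subgroup could be small. PN is also the only window with no upper limit. This is a reason to guard against imbalance combined with unequal spread, but it does not show that either will occur.

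At stake is whether a P value below 0.05 for inflammatory factor, albumin or defecation time across the feeding windows means what it appears to mean.

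**Working it through.** **Inputs from the documents.** Three groups (Study protocol); significance level 0.05 (Statistical analysis). The documents state no subgroup size, SD, total sample size or power, so there is no figure of the plan's own to reproduce.

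**Inputs assumed.** Sizes EEN/DEN/PN of 60/40/12 (total 112) and 50/40/20 (total 110); equal sizes of 40 or 20 each; one subgroup with 1.5, 2 or 3 times the SD of the other two; normal outcomes; no true difference in means.

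**Direction, by hand.** With k groups of sizes n_i, total N and SDs σ_i, and equal means:

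- E(MS between) = Σ(1 − n_i/N)σ_i² / (k − 1)
- E(MS within) = Σ(n_i − 1)σ_i² / (N − k)

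The ratio is 1 when the SDs are equal. With one SD doubled:

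- 60/40/12, PN SD doubled: between = (0.464 + 0.643 + 0.893 × 4)/2 = 2.34; within = (59 + 39 + 11 × 4)/109 = 1.30; ratio 1.80. The F statistic runs too high.
- 60/40/12, EEN SD doubled: between = (0.464 × 4 + 0.643 + 0.893)/2 = 1.70; within = (59 × 4 + 39 + 11)/109 = 2.62; ratio 0.65. It runs too low.
- 40/40/40, any one SD doubled: between = (2/3)(1 + 1 + 4)/2 = 2; within = 39 × 6/117 = 2; ratio 1.

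**Size, by simulation** (40,000 runs per scenario, rejection rate of classical ANOVA at nominal 5%):

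| Sizes EEN/DEN/PN | More variable subgroup | SD × 1.5 | SD × 2 | SD × 3 |
|---|---|---|---|---|
| 60/40/12 | PN (smallest) | 11.6% | 18.3% | 27.6% |
| 50/40/20 | PN (smallest) | 9.1% | 13.0% | 18.6% |
| 40/40/40 | PN | 5.1% | 5.9% | 7.2% |
| 20/20/20 | PN | 5.4% | 6.0% | 7.5% |
| 60/40/12 | EEN (largest) | 2.3% | 1.7% | not run |
| 50/40/20 | EEN (largest) | 3.5% | 2.8% | not run |

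Welch's ANOVA on the same normal data rejects in about 5% throughout. The table does not bound the effect: 70/40/10 with a PN SD ratio of 3 gives 31% to 32%, and 10/40/70 with the same ratio gives 0.6%.

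**Cost of Welch when SDs are equal.** For mean shifts of 0.6/0.3/0 SD, power goes from 46.5% to 43.9% (60/40/12, a loss of 2.6 points) and from 54.1% to 52.8% (50/40/20, a loss of 1.3 points).

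**Where Welch fails.** Lognormal outcomes with log-scale SD 1 (an assumption), equal means, sizes 60/40/12, 20,000 runs:

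| PN SD ratio | Classical ANOVA | Welch |
|---|---|---|
| 1 | 4.9% | 9.1% |
| 1.5 | 9.3% | 11.3% |
| 2 | 17.2% | 12.8% |

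With a small, strongly skewed subgroup, Welch over-rejects too, and at ratios 1 and 1.5 it does so more than classical ANOVA. Naming Welch alone would therefore be incomplete.

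**The case against.** A reader might infer that the plan commits to ordinary ANOVA for the subgroups. It does not. No test is tied to that comparison, and a Welch version is available within the one-way ANOVA procedure of the named software. This stands: ordinary ANOVA is the natural reading of the text, but it remains an inference. If the sponsor meant Welch, the same sentence settles it.

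A reader might also take 9% to 28% as this trial's error rate. That is not supported either. The figures come from assumed sizes and SD ratios, and nothing in the documents shows that the late-fed subgroup is small or more variable. An open-ended feeding window describes the grouping variable, not the spread of albumin or of an inflammatory marker. Other assumptions equally compatible with the text give close to 5%, or less.

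It is also fair to say that the plan separates normal from non-normal variables and names a nonparametric test, so skewed outcomes need not go to ANOVA. But Mann-Whitney compares two groups, which leaves a skewed outcome across three subgroups with no listed method.

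Finally, the consequence is limited. These are additional outcomes, and the primary endpoint, re-bleeding, is not analysed this way. What survives is that the direction of error cannot be known in advance, and that for normal outcomes a test is available that holds near 5% either way.

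**Conclusion.** The point holds in a conditional and limited form. The plan names one three-group method for quantitative data, gives it no protection against unequal spread, and applies it to subgroups whose sizes nobody controls.

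For normal outcomes, the nominal 5% becomes about 9% to 28% if a smallest subgroup of 12 or 20 in about 110 patients has 1.5 to 3 times the SD of the others. It is about 5% to 7.5% if sizes are equal. It is about 2% to 3.5% if the largest subgroup, at the same assumed sizes, has 1.5 to 2 times the SD. Which case applies cannot be told from the documents.

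The effect is confined to inflammatory factor, serum albumin and defecation time. Re-bleeding, mortality and the satisfaction rate are untouched. This is a worthwhile improvement, not a threat to the main conclusions.

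**What to change.** In Statistical analysis, add a sentence saying that approximately normal quantitative outcomes are compared across the three feeding-time subgroups by Welch's ANOVA, with Games-Howell for pairs, and non-normal ones by a three-group rank test such as Kruskal-Wallis. State in advance how each outcome is assigned to one route or the other.

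The rank test is needed because Mann-Whitney covers only two groups and because Welch can itself over-reject with a small, strongly skewed subgroup. A rank test compares distributions rather than means, so its result should be worded accordingly.

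The cost is a sentence or two of SAP text and no new data. Welch and Games-Howell are options in the software's one-way ANOVA procedure. The price is about 1 to 3 points of power if the variances are in fact equal. The change corrects the error rate only: the subgroups are not randomised, so differences between them would remain open to confounding.
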